Headache	Any Severity	xx (xx.x)	xx (xx.x)	xx (xx.x)	xx (xx.x)	xx (xx.x)
	0: None	xx (xx.x)	xx (xx.x)	xx (xx.x)	xx (xx.x)	xx (xx.x)
	1: Just Noticeable	xx (xx.x)	xx (xx.x)	xx (xx.x)	xx (xx.x)	xx (xx.x)
	2: Bothersome from Time to Time	xx (xx.x)	xx (xx.x)	xx (xx.x)	xx (xx.x)	xx (xx.x)
	3: Bothersome Most or All of the Time	xx (xx.x)	xx (xx.x)	xx (xx.x)	xx (xx.x)	xx (xx.x)
		Dry or Hacking Cough				
		Extent: 0 (Not at all)	1 (A little bit)	2 (Somewhat)	3 (Quite a bit)	4 (Very much)
Cough	Any Severity	xx (xx.x)	xx (xx.x)	xx (xx.x)	xx (xx.x)	xx (xx.x)
	0: None	xx (xx.x)	xx (xx.x)	xx (xx.x)	xx (xx.x)	xx (xx.x)
	1: Just Noticeable	xx (xx.x)	xx (xx.x)	xx (xx.x)	xx (xx.x)	xx (xx.x)
	2: Bothersome from Time to Time	xx (xx.x)	xx (xx.x)	xx (xx.x)	xx (xx.x)	xx (xx.x)

Symptom (Modified Jackson Score)	Maximum Severity	FLU-PRO Symptom and Maximum Extent n (%)				
		xx (xx.x)	xx (xx.x)	xx (xx.x)	xx (xx.x)	xx (xx.x)
	3: Bothersome Most or All of the Time	xx (xx.x)	xx (xx.x)	xx (xx.x)	xx (xx.x)	xx (xx.x)
		Wet or Loose Cough				
		Extent: 0 (Not at all)	1 (A little bit)	2 (Somewhat)	3 (Quite a bit)	4 (Very much)
Cough	Any Severity	xx (xx.x)	xx (xx.x)	xx (xx.x)	xx (xx.x)	xx (xx.x)
	0: None	xx (xx.x)	xx (xx.x)	xx (xx.x)	xx (xx.x)	xx (xx.x)
	1: Just Noticeable	xx (xx.x)	xx (xx.x)	xx (xx.x)	xx (xx.x)	xx (xx.x)
	2: Bothersome from Time to Time	xx (xx.x)	xx (xx.x)	xx (xx.x)	xx (xx.x)	xx (xx.x)
	3: Bothersome Most or All of the Time	xx (xx.x)	xx (xx.x)	xx (xx.x)	xx (xx.x)	xx (xx.x)
		Coughing				
		Extent: 0 (Never)	1 (Rarely)	2 (Sometimes)	3 (Often)	4 (Always)
Cough	Any Severity	xx (xx.x)	xx (xx.x)	xx (xx.x)	xx (xx.x)	xx (xx.x)
	0: None	xx (xx.x)	xx (xx.x)	xx (xx.x)	xx (xx.x)	xx (xx.x)
	1: Just Noticeable	xx (xx.x)	xx (xx.x)	xx (xx.x)	xx (xx.x)	xx (xx.x)
	2: Bothersome from Time to Time	xx (xx.x)	xx (xx.x)	xx (xx.x)	xx (xx.x)	xx (xx.x)
	3: Bothersome Most or All of the Time	xx (xx.x)	xx (xx.x)	xx (xx.x)	xx (xx.x)	xx (xx.x)
		Coughing Up Mucus or Phlegm				
		Extent: 0 (Never)	1 (Rarely)	2 (Sometimes)	3 (Often)	4 (Always)
Cough	Any Severity	xx (xx.x)	xx (xx.x)	xx (xx.x)	xx (xx.x)	xx (xx.x)
	0: None	xx (xx.x)	xx (xx.x)	xx (xx.x)	xx (xx.x)	xx (xx.x)
	1: Just Noticeable	xx (xx.x)	xx (xx.x)	xx (xx.x)	xx (xx.x)	xx (xx.x)
	2: Bothersome from Time to Time	xx (xx.x)	xx (xx.x)	xx (xx.x)	xx (xx.x)	xx (xx.x)
	3: Bothersome Most or All of the Time	xx (xx.x)	xx (xx.x)	xx (xx.x)	xx (xx.x)	xx (xx.x)
		Sleeping More Than Usual				
		Extent: 0 (Not at all)	1 (A little bit)	2 (Somewhat)	3 (Quite a bit)	4 (Very much)
Malaise (tiredness)	Any Severity	xx (xx.x)	xx (xx.x)	xx (xx.x)	xx (xx.x)	xx (xx.x)
	0: None	xx (xx.x)	xx (xx.x)	xx (xx.x)	xx (xx.x)	xx (xx.x)

Symptom (Modified Jackson Score)	Maximum Severity	FLU-PRO Symptom and Maximum Extent n (%)				
		xx (xx.x)	xx (xx.x)	xx (xx.x)	xx (xx.x)	xx (xx.x)
	1: Just Noticeable	xx (xx.x)	xx (xx.x)	xx (xx.x)	xx (xx.x)	xx (xx.x)
	2: Bothersome from Time to Time	xx (xx.x)	xx (xx.x)	xx (xx.x)	xx (xx.x)	xx (xx.x)
	3: Bothersome Most or All of the Time	xx (xx.x)	xx (xx.x)	xx (xx.x)	xx (xx.x)	xx (xx.x)
		Weak or Tired				
		Extent: 0 (Not at all)	1 (A little bit)	2 (Somewhat)	3 (Quite a bit)	4 (Very much)
Malaise (tiredness)	Any Severity	xx (xx.x)	xx (xx.x)	xx (xx.x)	xx (xx.x)	xx (xx.x)
	0: None	xx (xx.x)	xx (xx.x)	xx (xx.x)	xx (xx.x)	xx (xx.x)
	1: Just Noticeable	xx (xx.x)	xx (xx.x)	xx (xx.x)	xx (xx.x)	xx (xx.x)
	2: Bothersome from Time to Time	xx (xx.x)	xx (xx.x)	xx (xx.x)	xx (xx.x)	xx (xx.x)
	3: Bothersome Most or All of the Time	xx (xx.x)	xx (xx.x)	xx (xx.x)	xx (xx.x)	xx (xx.x)
		Body Aches or Pains				
		Extent: 0 (Not at all)	1 (A little bit)	2 (Somewhat)	3 (Quite a bit)	4 (Very much)
Body Ache	Any Severity	xx (xx.x)	xx (xx.x)	xx (xx.x)	xx (xx.x)	xx (xx.x)
	0: None	xx (xx.x)	xx (xx.x)	xx (xx.x)	xx (xx.x)	xx (xx.x)
	1: Just Noticeable	xx (xx.x)	xx (xx.x)	xx (xx.x)	xx (xx.x)	xx (xx.x)
	2: Bothersome from Time to Time	xx (xx.x)	xx (xx.x)	xx (xx.x)	xx (xx.x)	xx (xx.x)
	3: Bothersome Most or All of the Time	xx (xx.x)	xx (xx.x)	xx (xx.x)	xx (xx.x)	xx (xx.x)
		Chills or Shivering				
		Extent: 0 (Not at all)	1 (A little bit)	2 (Somewhat)	3 (Quite a bit)	4 (Very much)
Chills	Any Severity	xx (xx.x)	xx (xx.x)	xx (xx.x)	xx (xx.x)	xx (xx.x)
	0: None	xx (xx.x)	xx (xx.x)	xx (xx.x)	xx (xx.x)	xx (xx.x)
	1: Just Noticeable	xx (xx.x)	xx (xx.x)	xx (xx.x)	xx (xx.x)	xx (xx.x)
	2: Bothersome from Time to Time	xx (xx.x)	xx (xx.x)	xx (xx.x)	xx (xx.x)	xx (xx.x)
	3: Bothersome Most or All of the Time	xx (xx.x)	xx (xx.x)	xx (xx.x)	xx (xx.x)	xx (xx.x)
		Felt Cold				
		Extent: 0 (Not at all)	1 (A little bit)	2 (Somewhat)	3 (Quite a bit)	4 (Very much)

Symptom (Modified Jackson Score)	Maximum Severity	FLU-PRO Symptom and Maximum Extent n (%)				
		xx (xx.x)	xx (xx.x)	xx (xx.x)	xx (xx.x)	xx (xx.x)
Chills	Any Severity	xx (xx.x)	xx (xx.x)	xx (xx.x)	xx (xx.x)	xx (xx.x)
	0: None	xx (xx.x)	xx (xx.x)	xx (xx.x)	xx (xx.x)	xx (xx.x)
	1: Just Noticeable	xx (xx.x)	xx (xx.x)	xx (xx.x)	xx (xx.x)	xx (xx.x)
	2: Bothersome from Time to Time	xx (xx.x)	xx (xx.x)	xx (xx.x)	xx (xx.x)	xx (xx.x)
	3: Bothersome Most or All of the Time	xx (xx.x)	xx (xx.x)	xx (xx.x)	xx (xx.x)	xx (xx.x)
		Felt Hot				
		Extent: 0 (Not at all)	1 (A little bit)	2 (Somewhat)	3 (Quite a bit)	4 (Very much)
Feverish	Any Severity	xx (xx.x)	xx (xx.x)	xx (xx.x)	xx (xx.x)	xx (xx.x)
	0: None	xx (xx.x)	xx (xx.x)	xx (xx.x)	xx (xx.x)	xx (xx.x)
	1: Just Noticeable	xx (xx.x)	xx (xx.x)	xx (xx.x)	xx (xx.x)	xx (xx.x)
	2: Bothersome from Time to Time	xx (xx.x)	xx (xx.x)	xx (xx.x)	xx (xx.x)	xx (xx.x)
	3: Bothersome Most or All of the Time	xx (xx.x)	xx (xx.x)	xx (xx.x)	xx (xx.x)	xx (xx.x)
		Trouble Breathing				
		Extent: 0 (Not at all)	1 (A little bit)	2 (Somewhat)	3 (Quite a bit)	4 (Very much)
Shortness of Breath	Any Severity	xx (xx.x)	xx (xx.x)	xx (xx.x)	xx (xx.x)	xx (xx.x)
	0: None	xx (xx.x)	xx (xx.x)	xx (xx.x)	xx (xx.x)	xx (xx.x)
	1: Just Noticeable	xx (xx.x)	xx (xx.x)	xx (xx.x)	xx (xx.x)	xx (xx.x)
	2: Bothersome from Time to Time	xx (xx.x)	xx (xx.x)	xx (xx.x)	xx (xx.x)	xx (xx.x)
	3: Bothersome Most or All of the Time	xx (xx.x)	xx (xx.x)	xx (xx.x)	xx (xx.x)	xx (xx.x)

Notes: N = Number of infected participants in the Safety population; n = Number of participants reporting each symptom. Earache from Modified Jackson Score tool not included, with no corresponding FLU-PRO data for comparison.

Similar Table:

Table 42: Cross-Tabulation of the Maximum Severity of Solicited Influenza Symptoms and Participant-Reported FLU-PRO Symptoms During the Challenge Period, Uninfected Participants in the Safety Population

[Implementation Note: Update the footnote from the shell above for uninfected participants.]

Table 43: Summary of Symptom Scores by Challenge Dose Group and Infection Status, Safety Population

Symptom Score	Statistic	10 ⁴ TCID ₅₀ Challenge Virus (N=X)			10 ⁵ TCID ₅₀ Challenge Virus (N=X)			10 ⁶ TCID ₅₀ Challenge Virus (N=X)			Sham Inoculum (N=X)		
		Infected ^a	Uninfected	All Participants in Dose Group	Infected ^a	Uninfected	All Participants in Dose Group	Infected ^a	Uninfected	All Participants in Dose Group	Infected ^a	Uninfected	All Participants in Dose Group
Maximum Cumulative Modified Jackson Score (Total)	Mean (95% CI) ^b	x.x (x.x, x.x)	x.x (x.x, x.x)	x.x (x.x, x.x)	x.x (x.x, x.x)	x.x (x.x, x.x)	x.x (x.x, x.x)	x.x (x.x, x.x)	x.x (x.x, x.x)	x.x (x.x, x.x)	x.x (x.x, x.x)	x.x (x.x, x.x)	x.x (x.x, x.x)
	Minimum	XX	XX	XX	XX	XX	XX	XX	XX	XX	XX	XX	XX
	Median	XX	XX	XX	XX	XX	XX	XX	XX	XX	XX	XX	XX
	Maximum	XX	XX	XX	XX	XX	XX	XX	XX	XX	XX	XX	XX
Area Under the Modified Jackson Score Curve per Day (Days 2 through 8 for uninfected participants, or during infection for infected participants)	Mean (95% CI) ^b	x.x (x.x, x.x)	x.x (x.x, x.x)	x.x (x.x, x.x)	x.x (x.x, x.x)	x.x (x.x, x.x)	x.x (x.x, x.x)	x.x (x.x, x.x)	x.x (x.x, x.x)	x.x (x.x, x.x)	x.x (x.x, x.x)	x.x (x.x, x.x)	x.x (x.x, x.x)
	Minimum	XX	XX	XX	XX	XX	XX	XX	XX	XX	XX	XX	XX
	Median	XX	XX	XX	XX	XX	XX	XX	XX	XX	XX	XX	XX
	Maximum	XX	XX	XX	XX	XX	XX	XX	XX	XX	XX	XX	XX
Modified Jackson Score (Total), Study Day 15	Mean (95% CI) ^b	x.x (x.x, x.x)	x.x (x.x, x.x)	x.x (x.x, x.x)	x.x (x.x, x.x)	x.x (x.x, x.x)	x.x (x.x, x.x)	x.x (x.x, x.x)	x.x (x.x, x.x)	x.x (x.x, x.x)	x.x (x.x, x.x)	x.x (x.x, x.x)	x.x (x.x, x.x)
	Minimum	XX	XX	XX	XX	XX	XX	XX	XX	XX	XX	XX	XX
	Median	XX	XX	XX	XX	XX	XX	XX	XX	XX	XX	XX	XX
	Maximum	XX	XX	XX	XX	XX	XX	XX	XX	XX	XX	XX	XX
Cumulative FLU-PRO Score (Total)	Mean (95% CI)	x.x (x.x, x.x)	x.x (x.x, x.x)	x.x (x.x, x.x)	x.x (x.x, x.x)	x.x (x.x, x.x)	x.x (x.x, x.x)	x.x (x.x, x.x)	x.x (x.x, x.x)	x.x (x.x, x.x)	x.x (x.x, x.x)	x.x (x.x, x.x)	x.x (x.x, x.x)
	Minimum	XX	XX	XX	XX	XX	XX	XX	XX	XX	XX	XX	XX
	Median	XX	XX	XX	XX	XX	XX	XX	XX	XX	XX	XX	XX

Symptom Score	Statistic	10 ⁴ TCID ₅₀ Challenge Virus (N=X)			10 ⁵ TCID ₅₀ Challenge Virus (N=X)			10 ⁶ TCID ₅₀ Challenge Virus (N=X)			Sham Inoculum (N=X)		
		Infected ^a	Uninfected	All Participants in Dose Group	Infected ^a	Uninfected	All Participants in Dose Group	Infected ^a	Uninfected	All Participants in Dose Group	Infected ^a	Uninfected	All Participants in Dose Group
	Maximum	XX	XX	XX	XX	XX	XX	XX	XX	XX	XX	XX	XX
Cumulative FLU-PRO (Nose)	Mean (95% CI)	x.x (x.x, x.x)	x.x (x.x, x.x)	x.x (x.x, x.x)	x.x (x.x, x.x)	x.x (x.x, x.x)	x.x (x.x, x.x)	x.x (x.x, x.x)	x.x (x.x, x.x)	x.x (x.x, x.x)	x.x (x.x, x.x)	x.x (x.x, x.x)	x.x (x.x, x.x)
	Minimum	XX	XX	XX	XX	XX	XX	XX	XX	XX	XX	XX	XX
	Median	XX	XX	XX	XX	XX	XX	XX	XX	XX	XX	XX	XX
	Maximum	XX	XX	XX	XX	XX	XX	XX	XX	XX	XX	XX	XX
Cumulative FLU-PRO (Throat)	Mean (95% CI)	x.x (x.x, x.x)	x.x (x.x, x.x)	x.x (x.x, x.x)	x.x (x.x, x.x)	x.x (x.x, x.x)	x.x (x.x, x.x)	x.x (x.x, x.x)	x.x (x.x, x.x)	x.x (x.x, x.x)	x.x (x.x, x.x)	x.x (x.x, x.x)	x.x (x.x, x.x)
	Minimum	XX	XX	XX	XX	XX	XX	XX	XX	XX	XX	XX	XX
	Median	XX	XX	XX	XX	XX	XX	XX	XX	XX	XX	XX	XX
	Maximum	XX	XX	XX	XX	XX	XX	XX	XX	XX	XX	XX	XX
Cumulative FLU-PRO (Eyes)	Mean (95% CI)	x.x (x.x, x.x)	x.x (x.x, x.x)	x.x (x.x, x.x)	x.x (x.x, x.x)	x.x (x.x, x.x)	x.x (x.x, x.x)	x.x (x.x, x.x)	x.x (x.x, x.x)	x.x (x.x, x.x)	x.x (x.x, x.x)	x.x (x.x, x.x)	x.x (x.x, x.x)
	Minimum	XX	XX	XX	XX	XX	XX	XX	XX	XX	XX	XX	XX
	Median	XX	XX	XX	XX	XX	XX	XX	XX	XX	XX	XX	XX
	Maximum	XX	XX	XX	XX	XX	XX	XX	XX	XX	XX	XX	XX
Cumulative FLU-PRO (Chest/Respiratory)	Mean (95% CI)	x.x (x.x, x.x)	x.x (x.x, x.x)	x.x (x.x, x.x)	x.x (x.x, x.x)	x.x (x.x, x.x)	x.x (x.x, x.x)	x.x (x.x, x.x)	x.x (x.x, x.x)	x.x (x.x, x.x)	x.x (x.x, x.x)	x.x (x.x, x.x)	x.x (x.x, x.x)
	Minimum	XX	XX	XX	XX	XX	XX	XX	XX	XX	XX	XX	XX
	Median	XX	XX	XX	XX	XX	XX	XX	XX	XX	XX	XX	XX
	Maximum	XX	XX	XX	XX	XX	XX	XX	XX	XX	XX	XX	XX
Cumulative FLU-PRO (Body/Systemic)	Mean (95% CI)	x.x (x.x, x.x)	x.x (x.x, x.x)	x.x (x.x, x.x)	x.x (x.x, x.x)	x.x (x.x, x.x)	x.x (x.x, x.x)	x.x (x.x, x.x)	x.x (x.x, x.x)	x.x (x.x, x.x)	x.x (x.x, x.x)	x.x (x.x, x.x)	x.x (x.x, x.x)
	Minimum	XX	XX	XX	XX	XX	XX	XX	XX	XX	XX	XX	XX
	Median	XX	XX	XX	XX	XX	XX	XX	XX	XX	XX	XX	XX

Symptom Score	Statistic	10 ⁴ TCID ₅₀ Challenge Virus (N=X)			10 ⁵ TCID ₅₀ Challenge Virus (N=X)			10 ⁶ TCID ₅₀ Challenge Virus (N=X)			Sham Inoculum (N=X)		
		Infected ^a	Uninfected	All Participants in Dose Group	Infected ^a	Uninfected	All Participants in Dose Group	Infected ^a	Uninfected	All Participants in Dose Group	Infected ^a	Uninfected	All Participants in Dose Group
	Maximum	XX	XX	XX	XX	XX	XX	XX	XX	XX	XX	XX	XX
Cumulative FLU-PRO (Gastrointestinal)	Mean (95% CI)	x.x (x.x, x.x)	x.x (x.x, x.x)	x.x (x.x, x.x)	x.x (x.x, x.x)	x.x (x.x, x.x)	x.x (x.x, x.x)	x.x (x.x, x.x)	x.x (x.x, x.x)	x.x (x.x, x.x)	x.x (x.x, x.x)	x.x (x.x, x.x)	x.x (x.x, x.x)
	Minimum	XX	XX	XX	XX	XX	XX	XX	XX	XX	XX	XX	XX
	Median	XX	XX	XX	XX	XX	XX	XX	XX	XX	XX	XX	XX
	Maximum	XX	XX	XX	XX	XX	XX	XX	XX	XX	XX	XX	XX

Notes: N = Number of participants in the Safety population; GMT = Geometric Mean Titer; GMFR = Geometric Mean Fold-Rise. Cumulative FLU-PRO scores are the sum of the daily scores (based on maximum severity per question) across the entire challenge period.

^a RT-PCR+ results reported on at least two days during the challenge period (Days 2 to 8).

^b Confidence interval calculated based on the Student's t-distribution.

Table 44: Maximum Severity of Influenza Symptoms Reported During the Challenge Period by Clinical Site, Infected Participants in the Safety Population

Symptom	Severity	Duke University (N=X)		University of Maryland (N=X)	
		n (%)	95% CI	n (%)	95% CI
Any Symptom	Any Severity	x (x.x)	(x.x, x.x)	x (x.x)	(x.x, x.x)
	None	x (x.x)	-	x (x.x)	-
	Mild or Just Noticeable	x (x.x)	-	x (x.x)	-
	Moderate or Bothersome from Time to Time	x (x.x)	-	x (x.x)	-
	Severe or Bothersome Most or All of the Time	x (x.x)	-	x (x.x)	-
Runny Nose ^a	Any Severity	x (x.x)	(x.x, x.x)	x (x.x)	(x.x, x.x)
	0: None	x (x.x)	-	x (x.x)	-
	1: Just Noticeable	x (x.x)	-	x (x.x)	-
	2: Bothersome from Time to Time	x (x.x)	-	x (x.x)	-
	3: Bothersome Most or All of the Time	x (x.x)	-	x (x.x)	-
Stuffy Nose ^a	Any Severity	x (x.x)	(x.x, x.x)	x (x.x)	(x.x, x.x)
	0: None	x (x.x)	-	x (x.x)	-
	1: Just Noticeable	x (x.x)	-	x (x.x)	-
	2: Bothersome from Time to Time	x (x.x)	-	x (x.x)	-
	3: Bothersome Most or All of the Time	x (x.x)	-	x (x.x)	-
Sneezing ^a	Any Severity	x (x.x)	(x.x, x.x)	x (x.x)	(x.x, x.x)
	0: None	x (x.x)	-	x (x.x)	-
	1: Just Noticeable	x (x.x)	-	x (x.x)	-
	2: Bothersome from Time to Time	x (x.x)	-	x (x.x)	-
	3: Bothersome Most or All of the Time	x (x.x)	-	x (x.x)	-
Sore Throat ^a	Any Severity	x (x.x)	(x.x, x.x)	x (x.x)	(x.x, x.x)
	0: None	x (x.x)	-	x (x.x)	-
	1: Just Noticeable	x (x.x)	-	x (x.x)	-
	2: Bothersome from Time to Time	x (x.x)	-	x (x.x)	-
	3: Bothersome Most or All of the Time	x (x.x)	-	x (x.x)	-
Headache ^a	Any Severity	x (x.x)	(x.x, x.x)	x (x.x)	(x.x, x.x)

Symptom	Severity	Duke University (N=X)		University of Maryland (N=X)	
		n (%)	95% CI	n (%)	95% CI
	0: None	x (x.x)	-	x (x.x)	-
	1: Just Noticeable	x (x.x)	-	x (x.x)	-
	2: Bothersome from Time to Time	x (x.x)	-	x (x.x)	-
	3: Bothersome Most or All of the Time	x (x.x)	-	x (x.x)	-
Cough ^a	Any Severity	x (x.x)	(x.x, x.x)	x (x.x)	(x.x, x.x)
	0: None	x (x.x)	-	x (x.x)	-
	1: Just Noticeable	x (x.x)	-	x (x.x)	-
	2: Bothersome from Time to Time	x (x.x)	-	x (x.x)	-
	3: Bothersome Most or All of the Time	x (x.x)	-	x (x.x)	-
Malaise (tiredness) ^a	Any Severity	x (x.x)	(x.x, x.x)	x (x.x)	(x.x, x.x)
	0: None	x (x.x)	-	x (x.x)	-
	1: Just Noticeable	x (x.x)	-	x (x.x)	-
	2: Bothersome from Time to Time	x (x.x)	-	x (x.x)	-
	3: Bothersome Most or All of the Time	x (x.x)	-	x (x.x)	-
Body Ache ^a	Any Severity	x (x.x)	(x.x, x.x)	x (x.x)	(x.x, x.x)
	0: None	x (x.x)	-	x (x.x)	-
	1: Just Noticeable	x (x.x)	-	x (x.x)	-
	2: Bothersome from Time to Time	x (x.x)	-	x (x.x)	-
	3: Bothersome Most or All of the Time	x (x.x)	-	x (x.x)	-
Chills ^a	Any Severity	x (x.x)	(x.x, x.x)	x (x.x)	(x.x, x.x)
	0: None	x (x.x)	-	x (x.x)	-
	1: Just Noticeable	x (x.x)	-	x (x.x)	-
	2: Bothersome from Time to Time	x (x.x)	-	x (x.x)	-
	3: Bothersome Most or All of the Time	x (x.x)	-	x (x.x)	-
Feverish ^a	Any Severity	x (x.x)	(x.x, x.x)	x (x.x)	(x.x, x.x)
	0: None	x (x.x)	-	x (x.x)	-
	1: Just Noticeable	x (x.x)	-	x (x.x)	-
	2: Bothersome from Time to Time	x (x.x)	-	x (x.x)	-

Symptom	Severity	Duke University (N=X)		University of Maryland (N=X)	
		n (%)	95% CI	n (%)	95% CI
Fever ^b	3: Bothersome Most or All of the Time	x (x.x)	-	x (x.x)	-
	Any Severity	x (x.x)	(x.x, x.x)	x (x.x)	(x.x, x.x)
	None	x (x.x)	-	x (x.x)	-
	Mild	x (x.x)	-	x (x.x)	-
	Moderate	x (x.x)	-	x (x.x)	-
Shortness of Breath ^a	Severe	x (x.x)	-	x (x.x)	-
	Any Severity	x (x.x)	(x.x, x.x)	x (x.x)	(x.x, x.x)
	0: None	x (x.x)	-	x (x.x)	-
	1: Just Noticeable	x (x.x)	-	x (x.x)	-
	2: Bothersome from Time to Time	x (x.x)	-	x (x.x)	-
Earache ^a	3: Bothersome Most or All of the Time	x (x.x)	-	x (x.x)	-
	Any Severity	x (x.x)	(x.x, x.x)	x (x.x)	(x.x, x.x)
	0: None	x (x.x)	-	x (x.x)	-
	1: Just Noticeable	x (x.x)	-	x (x.x)	-
	2: Bothersome from Time to Time	x (x.x)	-	x (x.x)	-
Lymphopenia ^c	3: Bothersome Most or All of the Time	x (x.x)	-	x (x.x)	-
	Any Severity	x (x.x)	(x.x, x.x)	x (x.x)	(x.x, x.x)
	None	x (x.x)	-	x (x.x)	-
	Mild	x (x.x)	-	x (x.x)	-
	Moderate	x (x.x)	-	x (x.x)	-
	Severe	x (x.x)	-	x (x.x)	-

Notes: N = Number of participants in the Safety population with RT-PCR+ results on at least two study days; n = Number of participants reporting each symptom, regardless of timing with respect to RT-PCR positivity.

^a As reported on the Modified Jackson Score (MJS) tool; maximum severity across the challenge period reported.

^b As part of vital signs assessments, with temperature collected three times daily during the challenge period. Fever and feverishness (from MJS) contribute as one item towards the Modified Jackson Score.

^c As part of clinical safety laboratory assessments, on Study Days 2, 4, 8, and any supplemental visits during the challenge period.

Similar Table:

Table 45: Maximum Severity of Influenza Symptoms Reported During the Challenge Period by Clinical Site, Uninfected Participants in the Safety Population

Table 46: Symptoms Predicting Infection Status Lasso Logistic Regression Model to Predict Infection Status, Safety Population

Model Parameter	Parameter Estimate	SE	p-value	Odds Ratio	95% CI
Intercept	x.xx	x.xx	x.xxx	-	-
[Symptom x]	x.xx	x.xx	x.xxx	x.xx	(x.xx, x.xx)
[Symptom y]	x.xx	x.xx	x.xxx	x.xx	(x.xx, x.xx)

[Repeat for any additional symptom(s) selected in lasso procedure]

Notes: XX participants in the Safety population included in the model; the infection outcome is defined as two or more study days with RT-PCR+ tests at any point during the challenge period. The maximum severity of each MJS symptom during the infection period, or across the challenge period for the uninfected participants, is utilized in the set of candidate predictors.

The optimal value for the penalization parameter determined using 10-fold cross-validation.

Unbiased coefficient estimates obtained by refitting selected covariates in logistic regression model.

Hosmer and Lemeshow Goodness of Fit p-value = 0.xxx.

Table 47: Comparison of Symptomatic Influenza Infection to Mild-to-Moderate Influenza Disease, Safety Population

Variable	10 ⁴ TCID ₅₀ Challenge Virus (N=X)		10 ⁵ TCID ₅₀ Challenge Virus (N=X)		10 ⁶ TCID ₅₀ Challenge Virus (N=X)		Sham Inoculum (N=X)		All Participants (N=X)	
	MMID-2 n (%)	No MMID-2 n (%)	MMID-2 n (%)	No MMID-2 n (%)	MMID-2 n (%)	No MMID-2 n (%)	MMID-2 n (%)	No MMID-2 n (%)	MMID-2 n (%)	No MMID-2 n (%)
Symptomatic Influenza Infection	x (x.x)	x (x.x)	x (x.x)	x (x.x)	x (x.x)	x (x.x)	x (x.x)	x (x.x)	x (x.x)	x (x.x)
No Symptomatic Influenza Infection	x (x.x)	x (x.x)	x (x.x)	x (x.x)	x (x.x)	x (x.x)	x (x.x)	x (x.x)	x (x.x)	x (x.x)

Notes: N = Number of participants in the Safety population; n = Number of participants reporting the given combination of Symptomatic Influenza Infection and MMID-2 outcomes after challenge.

Table 48: Logistic Regression Model to Assess the Associations Between Baseline Characteristics and Development of Symptomatic Influenza Infection, Safety Population

Model Parameter	Parameter Estimate	SE	p-value	Odds Ratio	95% CI
Intercept	x.xx	x.xx	x.***	-	-
Challenge Virus Dose (TCID ₅₀)	x.xx	x.xx	x.***	x.xx	(x.xx, x.xx)
Age at Baseline (Years)	x.xx	x.xx	x.***	x.xx	(x.xx, x.xx)
Sex (Male vs. Female)	x.xx	x.xx	x.***	x.xx	(x.xx, x.xx)
Prior Receipt of Seasonal Influenza Vaccine or Viral Challenge (Yes vs. No)	x.xx	x.xx	x.***	x.xx	(x.xx, x.xx)
Clinical Site (UMD vs. DU)	x.xx	x.xx	x.***	x.xx	(x.xx, x.xx)

Notes: XX participants in the Safety population included in the model; the symptomatic influenza infection outcome is defined as two or more study days with RT-PCR+ tests and, separately, a cumulative Modified Jackson Score of at least 6 over any 5-day window during the challenge period. Hosmer and Lemeshow Goodness of Fit p-value = 0.xxx.

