3.2.3. Infection Status

Infection status, independent of symptom status, will be defined at the participant level in two different ways:

- Participants are considered **Infected** if viral shedding is detected in NP swab(s) by qualitative and/or quantitative RT-PCR on at least two days beginning 24 hours after challenge until Study Day 8
- Participants are considered to be **Currently Infected** from their first through their last study days meeting the viral shedding definition above (and in [Section 3.2.2](#)), regardless of any intermittent negative results between those two study days.

Pre-infection and post-infection results will be determined based on the definition of Current Infection above. New-onset symptoms will be those with a maximum severity post-infection (starting on the day of first RT-PCR positivity) above that of baseline, for infected participants.

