7.1.2. Influenza Symptoms

The maximum severity of influenza symptoms during the challenge period, reported as part of the Modified Jackson Score and used to determine the AR, will be summarized by challenge dose group in [Table 15](#), and separately by infection status (see [Section 3.2.3](#)) in [Table 16](#) and [Figure 7](#) (infected participants) and [Table 17](#) and [Figure 8](#) (uninfected participants). Symptoms reported on Study Day 15 will be presented similarly in [Table 18](#) and [Table 19](#). Symptoms over the challenge period will also be summarized by infection status, independent of challenge dose group, in [Table 20](#), and Day 15 symptoms will be presented in [Table 21](#).

New-onset symptoms (see [Section 3.2.3](#)) among infected participants will be summarized in [Figure 9](#), and the maximum severity of symptoms will be summarized by concurrent infection status in [Table 26](#). Wilcoxon signed rank tests will be used to compare maximum severities among infected participants: pre-infection to during infection, post-infection to during infection, and pre-infection to post-infection, in [Table 27](#). No p-value adjustment is planned for multiple comparisons, but the number of comparisons made will be considered when interpreting the results. Current/concurrent infection status is defined in [Section 3.2.3](#).

The maximum symptom severities reported for each study day during the challenge period and at any point post-challenge will be summarized for currently infected participants, separately by challenge dose group in [Table 22](#) through [Table 25](#). At baseline and Day 1, all participants will be included in these summaries, as a comparison for post-infection symptoms.

Total MJS scores during the challenge period will be presented by study day and challenge group in [Figure 10](#), with RT-PCR+ study days indicated with annotation in the given cell.

MJS symptoms will be presented in detail in [Listing 8](#).

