Notes: N = Number of participants in the Safety population RT-PCR+ on the given study day; n = Number of participants reporting each symptom. **Prior to Day 2, all participants included as symptom background.**

^a As reported on the Modified Jackson Score (MJS) tool.

^b As part of vital signs assessments, with temperature collected three times daily during the challenge period. Fever and feverishness (from MJS) contribute as one item towards the Modified Jackson Score.

^c As part of clinical safety laboratory assessments, on Study Days 2, 4, 8, and any supplemental visits during the challenge period.

Similar Tables:

Table 23: Maximum Severity of Participant-Reported Influenza Symptoms by Study Day, 10⁵ TCID₅₀ Challenge Virus Group, Currently Infected Participants in the Safety Population

Table 24: Maximum Severity of Participant-Reported Influenza Symptoms by Study Day, 10⁶ TCID₅₀ Challenge Virus Group, Currently Infected Participants in the Safety Population

Table 25: Maximum Severity of Participant-Reported Influenza Symptoms by Study Day, Sham Inoculum Group, Currently Infected Participants in the Safety Population

Table 26: Maximum Severity of Influenza Symptoms Reported During the Challenge Period by Current Infection Status, Safety Population

Symptom	Severity	Pre-Infection (N=X)		Current Infection (N=X)		Post-Infection (N=X)		Uninfected (N=X)	
		n (%)	95% CI	n (%)	95% CI	n (%)	95% CI	n (%)	95% CI
Any Symptom	Any Severity	x (x.x)	(x.x, x.x)	x (x.x)	(x.x, x.x)	x (x.x)	(x.x, x.x)	x (x.x)	(x.x, x.x)
	None	x (x.x)	-	x (x.x)	-	x (x.x)	-	x (x.x)	-
	Mild or Just Noticeable	x (x.x)	-	x (x.x)	-	x (x.x)	-	x (x.x)	-
	Moderate or Bothersome from Time to Time	x (x.x)	-	x (x.x)	-	x (x.x)	-	x (x.x)	-
	Severe or Bothersome Most or All of the Time	x (x.x)	-	x (x.x)	-	x (x.x)	-	x (x.x)	-
Runny Nose ^a	Any Severity	x (x.x)	(x.x, x.x)	x (x.x)	(x.x, x.x)	x (x.x)	(x.x, x.x)	x (x.x)	(x.x, x.x)
	0: None	x (x.x)	-	x (x.x)	-	x (x.x)	-	x (x.x)	-
	1: Just Noticeable	x (x.x)	-	x (x.x)	-	x (x.x)	-	x (x.x)	-
	2: Bothersome from Time to Time	x (x.x)	-	x (x.x)	-	x (x.x)	-	x (x.x)	-
	3: Bothersome Most or All of the Time	x (x.x)	-	x (x.x)	-	x (x.x)	-	x (x.x)	-
Stuffy Nose ^a	Any Severity	x (x.x)	(x.x, x.x)	x (x.x)	(x.x, x.x)	x (x.x)	(x.x, x.x)	x (x.x)	(x.x, x.x)
	0: None	x (x.x)	-	x (x.x)	-	x (x.x)	-	x (x.x)	-
	1: Just Noticeable	x (x.x)	-	x (x.x)	-	x (x.x)	-	x (x.x)	-
	2: Bothersome from Time to Time	x (x.x)	-	x (x.x)	-	x (x.x)	-	x (x.x)	-

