Notes: N = Number of participants in the Safety population reporting symptoms relevant to the given subgroup; n = Number of participants reporting each symptom, regardless of timing with respect to RT-PCR positivity. Uninfected participants include all those RT-PCR+ on no more than one study day.

^aAs reported on the Modified Jackson Score (MJS) tool; maximum severity across the challenge period reported.

^bAs part of vital signs assessments, with temperature collected three times daily during the challenge period. Fever and feverishness (from MJS) contribute as one item towards the Modified Jackson Score.

^cAs part of clinical safety laboratory assessments, on Study Days 2, 4, 8, and any supplemental visits during the challenge period.

Table 27: Paired Comparisons of Influenza Symptoms Reported Before, During, and After Infection, Infected Participants in the Safety Population

Symptom	Severity	Pre-Infection	Current Infection	Post-Infection	Pre-Infection vs. Current Infection	Pre-Infection vs. Post-Infection	Current Infection vs. Post-Infection
		n (%)	n (%)	n (%)	p-value ^d	p-value ^d	p-value ^d
Any Symptom	None	x (x.x)	x (x.x)	x (x.x)	0.xx	0.xx	0.xx
	Mild or Just Noticeable	x (x.x)	x (x.x)	x (x.x)	-	-	-
	Moderate or Bothersome from Time to Time	x (x.x)	x (x.x)	x (x.x)	-	-	-
	Severe or Bothersome Most or All of the Time	x (x.x)	x (x.x)	x (x.x)	-	-	-
Runny Nose ^a	0: None	x (x.x)	x (x.x)	x (x.x)	0.xx	0.xx	0.xx
	1: Just Noticeable	x (x.x)	x (x.x)	x (x.x)	-	-	-
	2: Bothersome from Time to Time	x (x.x)	x (x.x)	x (x.x)	-	-	-
	3: Bothersome Most or All of the Time	x (x.x)	x (x.x)	x (x.x)	-	-	-
Stuffy Nose ^a	0: None	x (x.x)	x (x.x)	x (x.x)	0.xx	0.xx	0.xx
	1: Just Noticeable	x (x.x)	x (x.x)	x (x.x)	-	-	-
	2: Bothersome from Time to Time	x (x.x)	x (x.x)	x (x.x)	-	-	-
	3: Bothersome Most or All of the Time	x (x.x)	x (x.x)	x (x.x)	-	-	-
Sneezing ^a	0: None	x (x.x)	x (x.x)	x (x.x)	0.xx	0.xx	0.xx
	1: Just Noticeable	x (x.x)	x (x.x)	x (x.x)	-	-	-
	2: Bothersome from Time to Time	x (x.x)	x (x.x)	x (x.x)	-	-	-
	3: Bothersome Most or All of the Time	x (x.x)	x (x.x)	x (x.x)	-	-	-
Sore Throat ^a	0: None	x (x.x)	x (x.x)	x (x.x)	0.xx	0.xx	0.xx
	1: Just Noticeable	x (x.x)	x (x.x)	x (x.x)	-	-	-

Symptom	Severity	Pre-Infection	Current Infection	Post-Infection	Pre-Infection vs. Current Infection	Pre-Infection vs. Post-Infection	Current Infection vs. Post-Infection
		n (%)	n (%)	n (%)	p-value ^d	p-value ^d	p-value ^d

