Symptom	Severity	Pre-Infection	Current Infection	Post-Infection	Pre-Infection vs. Current Infection	Pre-Infection vs. Post-Infection	Current Infection vs. Post-Infection
		n (%)	n (%)	n (%)	p-value ^d	p-value ^d	p-value ^d
Lymphopenia ^c	None	x (x.x)	x (x.x)	x (x.x)	0.xx	0.xx	0.xx
	Mild	-	-	-	-	-	-
	Moderate	-	-	-	-	-	-
	Severe	-	-	-	-	-	-

Notes: N = XX participants in the Safety population tested RT-PCR+ on at least two study days; n = Number of participants reporting each symptom within each timing category.

^aAs reported on the Modified Jackson Score (MJS) tool; maximum severity across the challenge period reported.

^bAs part of vital signs assessments, with temperature collected three times daily during the challenge period. Fever and feverishness (from MJS) contribute as one item towards the Modified Jackson Score.

^cAs part of clinical safety laboratory assessments, on Study Days 2, 4, 8, and any supplemental visits during the challenge period.

^dWilcoxon signed rank tests used to compare paired severities for each symptom, for infected participants.

Table 28: Qualitative and Quantitative RT-PCR Status During the Challenge Period by Study Day and Challenge Dose Group, Safety Population*

Study Day	Quantitative RT-PCR (RT-qPCR) Status	10 ⁴ TCID ₅₀ Challenge Virus (N=X)		10 ⁵ TCID ₅₀ Challenge Virus (N=X)		10 ⁶ TCID ₅₀ Challenge Virus (N=X)		Sham Inoculum (N=X)	
		Qualitative RT-PCR+ n (%)	Qualitative RT-PCR- n (%)	Qualitative RT-PCR+ n (%)	Qualitative RT-PCR- n (%)	Qualitative RT-PCR+ n (%)	Qualitative RT-PCR- n (%)	Qualitative RT-PCR+ n (%)	Qualitative RT-PCR- n (%)
Day 1 (Baseline)	RT-qPCR+	x (x.x)	x (x.x)	x (x.x)	x (x.x)	x (x.x)	x (x.x)	x (x.x)	x (x.x)
	Undetectable Virus	x (x.x)	x (x.x)	x (x.x)	x (x.x)	x (x.x)	x (x.x)	x (x.x)	x (x.x)
Day 2	RT-qPCR+	x (x.x)	x (x.x)	x (x.x)	x (x.x)	x (x.x)	x (x.x)	x (x.x)	x (x.x)
	Undetectable Virus	x (x.x)	x (x.x)	x (x.x)	x (x.x)	x (x.x)	x (x.x)	x (x.x)	x (x.x)
Day 3	RT-qPCR+	x (x.x)	x (x.x)	x (x.x)	x (x.x)	x (x.x)	x (x.x)	x (x.x)	x (x.x)
	Undetectable Virus	x (x.x)	x (x.x)	x (x.x)	x (x.x)	x (x.x)	x (x.x)	x (x.x)	x (x.x)
Day 4	RT-qPCR+	x (x.x)	x (x.x)	x (x.x)	x (x.x)	x (x.x)	x (x.x)	x (x.x)	x (x.x)
	Undetectable Virus	x (x.x)	x (x.x)	x (x.x)	x (x.x)	x (x.x)	x (x.x)	x (x.x)	x (x.x)
Day 5	RT-qPCR+	x (x.x)	x (x.x)	x (x.x)	x (x.x)	x (x.x)	x (x.x)	x (x.x)	x (x.x)
	Undetectable Virus	x (x.x)	x (x.x)	x (x.x)	x (x.x)	x (x.x)	x (x.x)	x (x.x)	x (x.x)

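### The notes under SAP Table 26, and footnote a of Table 27, ignore infection timing; followed literally, the tables cannot show a difference between infection phases

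*SAP*

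**What the plan says.** **Intended content.** SAP 7.1.2 states that "the maximum severity of symptoms will be summarized by concurrent infection status in" Table 26. SAP 3.2.3 treats a participant as currently infected from the first through the last day of detected shedding, whatever negatives fall between, and adds: "Pre-infection and post-infection results will be determined based on the definition of Current Infection above". The Table 26 shell follows this. Its columns are pre-infection, current infection, post-infection and uninfected, each with its own N.

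**Notes under Table 26.**
- Count: "n = Number of participants reporting each symptom, regardless of timing with respect to RT-PCR positivity".
- Denominator: "N = Number of participants in the Safety population reporting symptoms relevant to the given subgroup".
- Footnote a, attached to the Modified Jackson Score (MJS) items: "maximum severity across the challenge period reported".

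SAP 5.1 runs the challenge period from Day 1 to discharge, so it contains all three phases.

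**Notes under Table 27.** This table compares the same three phases in infected participants with Wilcoxon signed-rank tests. Its count is "n = Number of participants reporting each symptom within each timing category", but its footnote a is the same as that of Table 26.

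**The concern.** The column heads ask when a symptom occurred, and the notes tell the programmer to disregard when it occurred. The timing-free sentence also stands under Table 20 (columns by participant-level infection status) and Table 44 (columns by site). It fits there because those columns are not time phases. Under Table 26 it looks like carried-over text.

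Tables 26 and 27 cover the same phases, for infected participants, under opposite counting rules. If the notes are followed, Table 26 raises the background (pre-infection) column to the all-period level and hides the contrast it exists to show. In Table 27, footnote a would empty the paired tests on the MJS items.

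**Working it through.** Table 26 is an unfilled shell, so there is no stated figure to reproduce. The check applies the two counting rules side by side.

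**1. What each rule does.** For one infected participant and one symptom:
- Phase rule (SAP 3.2.3, Table 27 n note): three values, the maximum over the days before, during and after infection.
- Table 26 notes: one value, the maximum over Day 1 to discharge, entered in every phase column where the participant appears.

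A maximum over the whole period is never below the maximum over part of it. The literal rule can therefore only leave a phase count unchanged or raise it.

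**2. Illustration.** All inputs are assumed: observed Days 1 to 8, RT-PCR-positive Days 3 to 6, days independent, daily symptom probability p0 outside infection and p1 during it. That gives 2 pre-infection days, 4 infected days and 2 post-infection days.
- Pre or post by phase: 1 − (1 − p0)^2
- Current by phase: 1 − (1 − p1)^4
- Table 26 notes, any column: 1 − (1 − p0)^4 (1 − p1)^4

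For p0 = 0.10 and p1 = 0.50:
- pre or post: 1 − 0.81 = 0.19
- current: 1 − 0.0625 = 0.94
- notes: 1 − 0.6561 × 0.0625 = 0.96

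| p0 / p1 | Pre, by phase | Current, by phase | Post, by phase | Every column, by the notes |
|---|---|---|---|---|
| 0.05 / 0.30 | 10% | 76% | 10% | 80% |
| 0.10 / 0.50 | 19% | 94% | 19% | 96% |
| 0.20 / 0.60 | 36% | 97% | 36% | 99% |

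**3. Count check on invented data.** Take 20 invented infected participants and one symptom.
- All have the three phases: the notes give 20/20, 20/20 and 20/20; the phase rule gives 2/20, 19/20 and 4/20.
- Records stop at Day 8 and 3 of the 20 are still positive on that day: the notes give 20/20, 20/20 and 17/17; the phase rule gives 2/20, 19/20 and 1/17.

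In the second case the post-infection column differs under the notes only because 3 people leave it. Pre and current keep the same denominator because shedding counts from 24 hours after challenge, so Day 1 is pre-infection for everyone.

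**4. Table 27.** If each MJS item takes its challenge-period maximum in every phase, each within-person difference is zero and the signed-rank test has no non-zero pairs. The form has 12 MJS items and the table makes 3 comparisons, so 12 × 3 = 36 tests would be empty under the literal footnote. Fever and lymphopenia carry other footnotes and are not caught this way. In Table 26, by contrast, the n note covers every row.

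**The case against.** The strongest reply is that the intended analysis is not in doubt. The Table 26 title, its column heads with separate Ns, SAP 3.2.3 and SAP 7.1.2 all point to phase-specific results, and the N note refers to the given subgroup. A programmer following the text would produce correct counts under a wrong footnote. That is fair, and it limits the harm. It does not remove the error, because the published table would then misdescribe its own counts, and a programmer following the shell would get the wrong table.

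It is also true that neither table is marked for the topline report, and that the endpoints of primary objective 3 (total MJS and percentage symptomatic) do not depend on them.

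A reader might infer more than the documents support:
- *Table 26 is the only place where background is set beside infection symptoms.* It is not. Tables 22 to 25 print Baseline and Day 1 beside RT-PCR-positive days, Table 27 shows the same phases, and Figure 9 shows new-onset symptoms relative to baseline.
- *The N note makes the row for no symptoms impossible to fill.* That reading is strained. The MJS form records absence as level 0, and Tables 15 and 16 use similar wording for n beside rows for no symptoms.
- *Table 27 understates post-infection percentages because it prints one N.* This is not established. SAP 5.1 bases percentages on the non-missing sample size, and the documents do not say how many infected participants will lack a post-infection day.
- *All three infection columns must be identical.* The post-infection count can differ, because N is specific to the column.

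**Conclusion.** The point stands as an internal contradiction in the table shells. The Table 26 n note and footnote a conflict with its columns, with SAP 3.2.3 and 7.1.2, and with the Table 27 n note. Footnote a of Table 27 conflicts with the paired tests it sits under. This follows from the text and needs no assumptions.

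The size depends on a literal reading and on assumed symptom rates. Across the three scenarios the pre-infection column moves from 10–36% to 80–99%. The direction, never downward, holds for any rates.

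The consequence is modest. The tables sit under the primary clinical heading but are descriptive or exploratory, and they affect neither the attack rate nor dose selection. The correction should be made because the notes are wrong as written and cheap to change.

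**What to change.** **Table 26**
- In the n note, replace the timing-free clause with the counting rule from the Table 27 n note.
- Define N per column as participants with a non-missing assessment of the given item in that phase, consistent with SAP 5.1. The source is the MJS form, vital signs or the laboratory, as applicable. An N based on MJS assessments alone would not suit fever, which comes from vital signs, or lymphopenia, which comes from labs on Days 2, 4 and 8 and supplemental visits. A participant positive from Day 2, for example, has no scheduled post-challenge lab before infection.
- Change footnote a to the maximum severity within the given phase, keeping the challenge-period maximum for uninfected participants only.

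**Table 27**
- Change footnote a to the maximum severity within the given phase.
- Optionally print the non-missing n per phase.

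**Cost:** shell wording in the SAP. No new data and no protocol amendment.
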